3.1. Methodology

A single-centered, superiority, 2-arm, randomized controlled trial is planned to

determine the efficacy and safety of preoperative intravenous iron isomaltoside (Monofer®) therapy compared to standard care (control) in colorectal cancer patients undergoing elective tumour resection surgery. The study design is outlined in the diagram in Figure 1.

Figure 1. Overview of study design

For the pilot study to assess the feasibility of conducting the actual large-scale trial, 40 patients (20 in the treatment arm and 20 in the control arm) will be recruited. The study design of the pilot study would be identical to the above-proposed trial with the aim to explore the study process and the predicted effect size.

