3.6.1. Effect size

Primary Outcomes:

- Preoperative change in hemoglobin concentration (g/dL) and change in serum ferritin (mcg/L), which is, the difference between the value at diagnosis and preoperative day.

Secondary Outcomes:

- Units of red blood cells transfused in perioperative period in the two groups, defined as:
 1. Preoperative - from randomization to operation;
 2. Intraoperative – inside operating theatre and recovery room;
 3. Postoperative - from arrival to ward after operation to discharge.
- Duration of hospital stay (days).
- Quality of recovery as measured by questionnaire (QoR-15(Chinese)) completed on postoperative period. The QoR-15 (See Appendix A) includes the items measuring pain, physical comfort, physical independence, psychological support and emotional state.¹³ The QoR-15 score ranges from 0 to 150 and takes about 3 minutes to complete.¹³ The validity (convergent, construct, discriminant), reliability (internal consistency, split-half, test-retest), responsiveness,

acceptability and feasibility properties have been well established.¹³

- Incidence of adverse reactions/serious adverse events to intravenous iron administration and adverse reaction to blood transfusions (Adverse reactions: any unintended responses related to drug/blood products administrations e.g. skin rash, pain, neurological/respiratory/cardiovascular symptoms. Serious adverse events: life-threatening/require additional period of hospitalization/results in disability/mortality eg. Anaphylaxis, acute hemolytic transfusion reactions, organ failure etc.).
- Rate of surgical complications recorded and graded according to Clavien Classification of Surgical Complications.¹⁴ (See Appendix B)
- Days (alive and) at home within 30 days of surgery (DAH₃₀)
 - A parameter incorporating the duration of initial hospital stay associated with the index surgery, re-hospitalization due to post-discharge complications, discharge to institutional care and early deaths within 30 days post operatively. It has been validated as an effective patient-centered outcome measure for perioperative trials.¹⁵
 - Method of calculation – refer to Appendix C

3.6.2. Study process:

- Patient recruitment rate (number of recruited patient/total number of eligible patients x 100%)
- Number of patients recruited per month.
- Median waiting time to surgery (days).

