3.7. Randomization, allocation concealment and blinding

Recruited patients would be prospectively randomized to either preoperative intravenous iron isomaltoside (treatment group) or standard care (control group). The 1:1 allocation will be performed by one of the investigators, not involved in patient care or study assessment, using a computer program PASS 14.0 (NCSS, Kaysville, UT). The treatment allocation will be concealed in sealed opaque envelopes and handed over to third party anaesthetists (other than the investigators) for arranging pre-operative

intravenous iron therapy for patients in the treatment arm, or no therapy in the control arm.

Records related to the iron administration will be kept away from the investigators and the parent surgical team for the duration of the study period to reduce performance bias. Patients in both arms will not be blinded to the treatment they may receive in the management of perioperative anaemia, be it intravenous iron in the treatment group, or any necessary perioperative blood transfusions in either groups. An alert in the patient's electronic records will be implemented to remind the parent surgical team and the case anaesthetist that the patient is participating the study, however the both parties will be blinded to the patients' group assignment, to avoid interference to their transfusion decision.

Unblinding will be done only in the condition where clinician believes that clinical management depends importantly on whether the patient received intravenous ferric isomaltoside. Unblinding will be achieved by contacting the investigators, and any unblinding event and the reason of unblinding will be recorded.

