3.10. Intervention: intravenous iron isomaltoside(Monofer®)

Patients randomized to the treatment group will be given a dose of intravenous iron isomaltose in the time frame of 3-10 weeks before operation date. The dose will be determined by the patient's body weight: > 50kg: 1000mg; <50kg: 20mg/kg body weight, to be infused over 30 minutes. The infusion would take place in the day surgical unit and patients will be closely monitored. Vital signs would be charted before, at 15 minutes during infusion and immediately after the infusion. Patients will be discharged home on the same day if no adverse reactions are observed.

2 weeks after intravenous iron isomaltoside administration, blood test for hemoglobin level and iron profile would be repeated. Subjects with hemoglobin level less than 10g/dL will receive a second dose of intravenous iron isomaltoside. The second dose would be identical to the first dose i.e. body weight: > 50kg: 1000mg; <50kg: 20mg/kg body weight, to be infused over 30 minutes. Similar as before, intravenous iron administration would take place during a day admission to the day surgical unit with monitoring.

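### The drug-safety outcome is worded as events due to iron, so its iron part is zero by definition in control, and serious events of other causes before surgery are compared nowhere

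*Combined protocol and SAP*

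**What the plan says.** Section 3.1 describes a trial to "determine the efficacy and safety of preoperative intravenous iron isomaltoside (Monofer®) therapy compared to standard care (control"), and adds of the pilot: "The study design of the pilot study would be identical to the above-proposed trial". The only outcome aimed at drug safety is a secondary outcome in section 3.6.1: "Incidence of adverse reactions/serious adverse events to intravenous iron administration and adverse reaction to blood transfusions".

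The bracket after it defines the two terms differently. Adverse reactions are "any unintended responses related to drug/blood products administrations", so a causal link is required. The other definition reads "Serious adverse events: life-threatening/require additional period of hospitalization/results in disability/mortality", which sets a threshold of severity and says nothing about cause.

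Sections 3.9 and 3.11 rule out other iron supplements after recruitment and intravenous iron in control. Section 3.10 places the infusion 3-10 weeks before the operation. Section 3.6.1 also lists Clavien-graded surgical complications and DAH30. Section 3.12 has the investigators collect outcomes from Hospital Authority computer records and ward documents. Section 4 gives a general chi-square rule for categorical data and does not mention the safety item.

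**The concern.** A comparison of safety with standard care needs an outcome that can occur in both arms. An event counted because it is due to iron can occur only where iron was given. The control count for that part is therefore set by the definition, and the difference between arms can never be negative. It is an incidence among treated patients, not a treatment comparison.

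Patients awaiting colorectal cancer surgery can also have serious events for other reasons, such as tumour bleeding, infection or a cardiac event. Iron could raise or lower the rate of some of these without anyone blaming iron for the individual case. Section 6.1 itself raises infection as a possible effect before discounting it. If the item is tabulated as worded, a reader may take few or no iron events as evidence of safety against standard care, although that comparison was not made. If it is tabulated by the bracketed SAE definition, the table is a different one. The plan should say which applies.

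**Working it through.** The plan states no figure to reproduce here. The check is which serious events are counted, in which arm and when, followed by what an all-cause count would deliver.

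**Step 1: coverage, on the wording of the outcome.**

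| Serious event | Iron arm | Control arm | Source |
|---|---|---|---|
| Before surgery, attributed to iron | counted | cannot occur | 3.6.1, 3.9, 3.11 |
| Before surgery, reaction to transfusion | counted | counted | 3.6.1 |
| Before surgery, any other cause | not counted | not counted | 3.6.1 |
| After surgery, any cause | Clavien, DAH30 | Clavien, DAH30 | 3.6.1, Appendices B and C |

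Clavien grades departures from the normal postoperative course, and DAH30 starts at the index surgery (Day 0). Neither reaches back before the operation. The third row is the gap. The first row is the structural zero: 0 of 20 in control, assuming no off-protocol iron.

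**Step 2: the other reading.** If the bracketed SAE definition governs alone, the third row is counted in both arms and the zero disappears. Nothing in section 3.12 or section 4 says that serious events before surgery are to be sought in both arms, so this reading has no collection plan behind it.

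**Step 3: how many events fall in the gap.** The documents give no preoperative all-cause rate. Assume 5% to 10% per arm, with 20 patients per arm (section 3.1).

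- Expected per arm: 20 × 0.05 = 1 and 20 × 0.10 = 2 patients.
- Chance of at least one among 40: 1 - 0.95^40 = 0.871 and 1 - 0.90^40 = 0.985.

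**Step 4: precision of an all-cause count.** Take 2/20 v 1/20 as an example, with Newcombe's interval built from Wilson limits.

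- Wilson 95% limits: 2/20 gives 0.028 to 0.301; 1/20 gives 0.009 to 0.236.
- Difference: 0.10 - 0.05 = +0.05.
- Lower limit: 0.05 - √[(0.10 - 0.028)² + (0.236 - 0.05)²] = -0.15.
- Upper limit: 0.05 + √[(0.301 - 0.10)² + (0.05 - 0.009)²] = +0.26.

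An all-cause count is a genuine comparison, but with 40 patients it can only be descriptive.

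**The case against.** Several parts of the opposing case stand. Reporting reactions among those exposed is ordinary practice, and it is kept below. Harm after surgery, including death, is compared in both arms whatever its cause. The pilot's stated purpose is feasibility (section 2), and 40 patients cannot establish safety under any definition. What these points leave open is the period before surgery, where nothing is compared.

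Four stronger readings are tempting, and the documents do not support them.

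- **The SAE result is all but fixed at 0 v 0.** Section 6.1 quotes 38 serious events per million administrations. Over 20 to 40 doses that gives 1 - (1 - 0.000038)^20 = 0.08% to 1 - (1 - 0.000038)^40 = 0.15% for any event. But this holds only if the outcome wording overrides the bracketed definition and attribution follows that rate. If 10% of iron patients had a serious event and half were put down to iron (both assumed), the chance of at least one recorded iron SAE would be 1 - 0.95^20 = 64%.
- **Blinding makes attribution impossible.** Iron records are "kept away from the investigators and the parent surgical team for the duration of the study period", so the restriction is limited in time. Infusions are monitored, and section 3.10 says: "Patients will be discharged home on the same day if no adverse reactions are observed". Third-party anaesthetists arrange the therapy. Section 3.7 also allows for clinical need: "Unblinding will be done only in the condition where clinician believes that clinical management depends importantly on whether the patient received intravenous ferric isomaltoside". What is missing is a written step for handing the reactions over.
- **The chi-square test will be run against the fixed zero.** Section 3.6.1 specifies the two groups for transfusion units but gives only an incidence here, and the section 4 rule is general. Such a test is possible, not stated.
- **The rule will carry into the larger trial.** Section 3.1 calls the designs identical, but section 5 says the pilot serves to refine the design.

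**Conclusion.** The point holds as a minor one. On its own wording, the iron part of the safety outcome is zero by definition in control and gives no comparison with standard care. The SAE definition beside it leaves the intended scope unclear. The practical loss is serious events of any cause from randomisation to surgery: about 1-2 patients per arm if 5-10% are affected, a range that is assumed. No primary outcome and no feasibility criterion is touched. The conclusion does not depend on the rates quoted in section 6.1 or on any assumption about how readily events are blamed on iron.

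**What to change.** Split the item in section 3.6.1.

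- **(a) Infusion and transfusion reactions.** Report patients affected among those who received iron or blood, descriptively. The day unit and the third-party anaesthetists record infusion reactions and pass them on after outcome collection ends.
- **(b) SAEs.** Use the protocol's own seriousness criteria, whatever the suspected cause, in both arms, from randomisation to 30 days after surgery. The planned infusion-day and index-surgery admissions do not count. A reaction that turns an infusion visit into an unplanned stay does count, and joins (b) when (a) is handed over.

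In section 4, report (b) as patients with at least one event by randomised arm, before and after surgery separately, with risk difference and 95% CI. Exempt both items from the chi-square rule.

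In section 3.12, find the events by the same search of Hospital Authority admission and death records in both arms. Have the infusion-day entries removed before the investigators classify the rest. Do not rely on a list compiled by staff who know the allocation, since that would bias ascertainment and give them a new duty. Leave Clavien and DAH30 as they are.

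The cost is a few reworded sentences and some extra record review for 40 patients, with no new visit or test. Two limits remain. Iron patients have an infusion visit and, as section 3.10 is written, a 2-week blood test that control patients lack, so detection before surgery is not fully equal. Care outside the Hospital Authority system is missed in both arms. With the imprecision shown above, the comparison should be labelled descriptive.

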3.7. Randomization, allocation concealment and blinding

Recruited patients would be prospectively randomized to either preoperative intravenous iron isomaltoside (treatment group) or standard care (control group). The 1:1 allocation will be performed by one of the investigators, not involved in patient care or study assessment, using a computer program PASS 14.0 (NCSS, Kaysville, UT). The treatment allocation will be concealed in sealed opaque envelopes and handed over to third party anaesthetists (other than the investigators) for arranging pre-operative

intravenous iron therapy for patients in the treatment arm, or no therapy in the control arm.

Records related to the iron administration will be kept away from the investigators and the parent surgical team for the duration of the study period to reduce performance bias. Patients in both arms will not be blinded to the treatment they may receive in the management of perioperative anaemia, be it intravenous iron in the treatment group, or any necessary perioperative blood transfusions in either groups. An alert in the patient's electronic records will be implemented to remind the parent surgical team and the case anaesthetist that the patient is participating the study, however the both parties will be blinded to the patients' group assignment, to avoid interference to their transfusion decision.

Unblinding will be done only in the condition where clinician believes that clinical management depends importantly on whether the patient received intravenous ferric isomaltoside. Unblinding will be achieved by contacting the investigators, and any unblinding event and the reason of unblinding will be recorded.

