transfusion rate and hospital stay is thus expected, which implies that a large sample size would be required to conduct a RCT with adequate statistical power. Before embarking on such a large-scale research project, it is necessary to conduct a feasibility trial to estimate recruitment rate, sample size and allow proper logistics management.

There are two areas to be assessed in this pilot trial including study process and the predicted effect size.

2.1. Study process:

The number of patients diagnosed with colorectal cancer listed for elective resection per month will be studied, and the prevalence of iron deficiency anaemia among these patients will be recorded. All of the eligible patients satisfying the recruitment criteria stated below would be invited to join the pilot study, and the refusal rate will be noted. The information is required to calculate the recruitment rate of the study. The median waiting time for surgery will also be calculated. We envision that a recruitment rate of more than 60%, 5 patients per month and a median waiting time of 4 weeks will be necessary for conducting a larger RCT.

2.2. Effect size:

In this pilot trial, we plan to explore the effect size of the primary outcomes for the proposed RCT, including haemoglobin rise and serum ferritin rise associated with the intravenous iron treatment group compared to standard care. The secondary outcomes to be measured will include perioperative blood transfusion rate, hospital length of stay, quality of recovery scores, surgical complications, adverse reactions and days (alive and) at home within 30 days of surgery (DAH₃₀). As stated before, the baseline transfusion rate for elective colorectal surgeries in our population is lower compared to international studies, therefore it would be inaccurate to use existing data to estimate the sample size.

[figure not shown]
3. Study Design

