3.12. Follow up/assessment

Data on the primary and secondary outcomes as listed above would be collected. Investigators will access the patients' records via the Hospital Authority computer system and the hardcopy documents in the wards. Data on the hematological profile throughout study period (on diagnosis, preoperative day, post-operation day one, on discharge) will be retrieved from the computer records. The number of red cell transfusion will be retrieved from the computer records as well as counterchecking with

anaesthetic records/progress notes. The length of hospital stay (for the operation and DAH₃₀) will be counted by referring to computer patient records.

The quality of recovery is assessed by a self-reported quality of recovery questionnaire (QoR-15)¹³, which assess different dimensions of recovery including pain, physical comfort, physical independence and mental well-being.

4. Statistical analysis

Missing data will be checked and imputed to preserve power. The Shapiro-Wilk test will be used to check data for normality. Generalized estimating equations will be used to examine the changes in haemoglobin level and serum ferritin levels over time. Expected skewed data, such as the quality of recovery score, the number of days of hospital stay, units of transfusion and DAH₃₀, will be reported as median and interquartile range, and compared between treatment arms by Mann-Whitney U tests. Two-tailed χ^2 test will be used to analyze categorical data between groups. All of the analysis would be intention-to-treat and with a statistical significance level defined at $P < 0.05$.

5. Expected impact on study/patient care

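### Section 3.7 names no blocking or stratification and section 4 no adjustment for baseline haemoglobin, so at n=40 a chance imbalance in haemoglobin passes unadjusted into the secondary comparisons

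*Combined protocol and SAP*

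**What the plan says.** **Allocation.** Section 3.7 states: "The 1:1 allocation will be performed by one of the investigators, not involved in patient care or study assessment". The software is PASS 14.0. On concealment it adds: "The treatment allocation will be concealed in sealed opaque envelopes and handed over to third party anaesthetists". No section gives the algorithm, a block size, a stratification factor or the length of the list.

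**Arm sizes.** Section 3.1 states: "40 patients (20 in the treatment arm and 20 in the control arm) will be recruited".

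**Baseline haemoglobin.** Section 3.3 admits any value below 13 g/dL, with no lower limit, so haemoglobin is known before randomisation. Section 3.8 has it recorded.

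**Where haemoglobin affects care.** Section 3.10, for the test two weeks after the first infusion in the treatment arm: "Subjects with hemoglobin level less than 10g/dL will receive a second dose of intravenous iron isomaltoside". Section 3.9 leaves transfusion to the clinical judgment of blinded teams and sets no trigger.

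**Analysis.** Section 4 expects quality of recovery, stay, units transfused and DAH30 to be skewed, to be "compared between treatment arms by Mann-Whitney U tests". Haemoglobin and ferritin over time go into generalized estimating equations. No baseline covariate or stratified test is named for any outcome.

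**The concern.** A prognostic variable that is known before randomisation can be balanced in the design, used in the analysis, or both. The plan does neither for haemoglobin. Starting haemoglobin plausibly affects whether a patient is transfused, and through that perhaps stay and recovery. With about 20 patients per arm, one arm can hold several more severely anaemic patients by chance, and an unadjusted rank test has no means of allowing for it.

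At stake is the precision and readability of the comparisons of transfusion, stay, DAH30 and QoR-15. Section 2 gives the small expected effects on transfusion and stay as the reason a large trial is needed. For transfusion, section 2.2 says of outside sources that "it would be inaccurate to use existing data to estimate the sample size", so the pilot's own estimates will carry weight. Section 3.1 makes the pilot's design identical to that of the proposed trial, so an undescribed allocation method and an unadjusted analysis could carry forward.

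**Working it through.** **Inputs from the documents:** N = 40, 20 per arm, 1:1 (sections 3.1 and 3.7). The plan gives no SD, effect size or power, so there is no sample size calculation to reproduce; 20 + 20 = 40 agrees with 1:1.

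**Assumed inputs (not in the documents):** haemoglobin SD of 1.0 to 2.0 g/dL; 20% to 50% of patients below 10 g/dL; transfusion risks below/above 10 g/dL from 15%/5% to 40%/5%.

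**1. Arm sizes, if the list were simple 1:1 randomisation** (the text neither says nor excludes this)
- P(exactly 20/20) = C(40,20)/2^40 = 12.5%.
- P(24/16 or more uneven) = 26.8%.
- Cost of 24/16: effective N = 4 × 24 × 16/40 = 38.4, so the SE rises by √(40/38.4) − 1 = 2.1%.

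A fixed list of 20 + 20, or unstratified blocks of a size dividing 40, would give 20/20 with certainty once all 40 places are used.

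**2. Chance imbalance in mean haemoglobin at exactly 20/20**
- SE of the difference = SD × √(1/20 + 1/20) = 0.316 SD.
- 95% limits = ±1.96 × 0.316 = ±0.62 SD.
- P(difference beyond 0.5 SD) = 11.4%.
- For an assumed SD of 1.0, 1.5 or 2.0 g/dL the limits are ±0.62, ±0.93 or ±1.24 g/dL.
- At 24/16 the SE is 0.323 SD, almost the same. Equal arm sizes do not address haemoglobin balance.

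**3. Chance imbalance in the number of low-haemoglobin patients.** Let m of the 40 be below 10 g/dL, with arms fixed at 20/20 (hypergeometric):

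| Assumed share | m | P(arms differ by 4 or more) |
|---|---|---|
| 20% | 8 | 23.5% |
| 30% | 12 | 30.1% |
| 40% | 16 | 33.3% |
| 50% | 20 | 34.3% |

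Under simple randomisation the range is 29% to 50%. With blocks of 2 and 4 within two haemoglobin strata the arms differ by at most 2 such patients.

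**4. What an imbalance does.** Take 8 against 4 low-haemoglobin patients and assumed risks of 40%/5%. The transfusion risk difference shifts by (8 − 4)/20 × (0.40 − 0.05) = 7 percentage points with no treatment effect.

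**5. Precision available from using haemoglobin**, for an assumed share of 30%. The unadjusted variance is 2p(1 − p)/20, where p is the overall risk. The stratified variance is 2[0.3·a(1 − a) + 0.7·b(1 − b)]/20, where a and b are the risks below and above 10 g/dL.

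| a/b | p | p(1 − p) | Within-stratum | Variance reduction |
|---|---|---|---|---|
| 40%/5% | 0.155 | 0.1310 | 0.1053 | 19.6% |
| 20%/2% | 0.074 | 0.0685 | 0.0617 | 9.9% |
| 20%/5% | 0.095 | 0.0860 | 0.0813 | 5.5% |
| 15%/5% | 0.080 | 0.0736 | 0.0715 | 2.9% |

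At 40%/5% the SE falls from √(2 × 0.1310/20) = 0.114 to √(2 × 0.1053/20) = 0.103.

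**6. Analysis or allocation?** In simulation at 40%/5% with an ordinary unstratified 20/20 list, the SE is 0.115 unadjusted and 0.103 to 0.106 when adjusted for stratum, depending on the method. Stratified blocks give 0.102 to 0.103. Adjustment alone captures most of the gain.

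**7. What stratified blocks do to arm sizes.** The last block in each stratum may be incomplete. In simulation, with blocks of 4 or of 2 and 4, exactly 20/20 occurs in about 62% to 65% of trials; the worst case is 18/22.

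**The case against.** The case on the other side has real force.

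- **A reader might infer that the list is plain 1:1 and cannot deliver 20/20.** The documents do not support that. Section 3.7 is silent on method, and a fixed 20 + 20 list would fit it and section 3.1 together. The 12.5% figure holds only if simple randomisation is assumed, and uneven arms cost little. What stands is that the text does not assure 20/20.
- **A reader might infer that baseline haemoglobin is shown to be a main driver of second doses and transfusion.** It is not. The 10 g/dL threshold in section 3.10 applies to the two-week test in the treatment arm, and section 3.9 defines no transfusion trigger. An influence of baseline haemoglobin is plausible but not quantified.
- **Chance imbalance is not bias.** The test's error rate already allows for it, and the 7-point shift is about 0.6 of the SE (0.07/0.114). This stands. The loss is in precision and interpretation.
- **The outcomes most exposed are secondary.** Section 5 bases the later sample size on the primary outcomes, which are changes from baseline. This reduces the weight of the point. It does not remove it, because change usually correlates with the starting value, so a baseline imbalance can shift the primary comparison too.
- **The precision gain may be small.** This also stands. Section 1 describes a local transfusion rate much lower than in published series, so the lower rows of the last table are plausible. That calculation also uses a binary risk, whereas the planned outcome is units compared by ranks.

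**Conclusion.** The concern holds as a low-cost improvement. The plan describes no restriction or stratification of the sequence and no use of baseline haemoglobin in any analysis, although the value is available for every patient before randomisation. Chance differences of up to about 0.62 SD in mean haemoglobin are to be expected at 20/20, and the planned Mann-Whitney tests do not correct for them.

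The 0.62 SD figure needs no assumption beyond 20 per arm and a normal approximation. The gain from acting does rest on assumptions: about 3% to 20% lower variance of the transfusion risk difference over the inputs used here, with 20% the favourable end. The finding does not show that the trial is biased, that the arms will be unequal, or that stratified allocation is essential.

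**What to change.** **Main change, section 4.** Compare units transfused, stay, DAH30 and QoR-15 with a Mann-Whitney test stratified by baseline haemoglobin (van Elteren), or with another prespecified method that adjusts for it. Include baseline haemoglobin in the haemoglobin and ferritin GEE models, and state whether the baseline measurement enters each model as a covariate or as one of the repeated responses, so that it is not used as both. Fix the stratum boundary in advance. The 10 g/dL value used above is only a convenient analysis cut-off; nothing here bears on the dosing rule.

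**Secondary change, section 3.7.** State how the sequence is generated: random permuted blocks of varying size, with the sizes withheld from recruiters. Optionally run them within two baseline haemoglobin strata, with a separate numbered envelope set for each. At n=40, use no more than one stratification factor.

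**Cost.** A few sentences and, if strata are used, one more list input and a second envelope set. No extra patients, visits or tests are needed. There is a small loss of efficiency if haemoglobin proves not to be prognostic. Stratified blocks may finish as uneven as 18/22, so section 3.1 should then give 20 per arm as a target. The allocation change must be made before the first randomisation; the analysis change should be fixed before outcome data are seen by arm.
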